**FORM: Application for Human Research**

NUMBER	FORM DATE	PAGE
F200		11 of 18

patient reported outcome measures assessing pain, function and level of activity. Subjects will complete validated patient reported outcome questionnaires assessing pain, function and level of activity prior to initiating treatment and at 0, 2, 4, 6, 12, and 24 weeks after starting treatment.

Pain will be assessed using the of the foot function index pain subscale (FFI-P) and the subject reported outcome measures (SROM). These two instruments have been used to assess pain in previous studies of plantar fascia treatments. (Please see Appendices 1-D and 1-E of the Protocol.)

Function will be assessed using two validated PRO instruments the PROMIS PF CAT and the FAAM. The PROMIS PFCAT is a subject relevant outcome measure that uses computer adaptive survey questions to assess the patient's pain and function in relation to daily activities. (Please see Appendix 1-A of the Protocol.) The FAAM has been shown to be a reliable, responsive, and valid measure of physical function for individuals with a broad range of musculoskeletal disorders of the lower leg, foot, and ankle. (Please see Appendix 1-B of the Protocol.)

Level of Activity will be assessed using the activity subscale of FAAM. This subscale scores quantitatively the level of difficulty subjects often face when they perform basic activities of daily living. It has shown to be an accurate and reliable predictor of the activity level while performing day-to-day activities. (Please see Appendix 1-B of the Protocol.)

Diagnostic Ultrasound (Aim 2). Diagnostic ultrasound will be utilized to compare the changes in plantar fascia thickness that occurs over time in subjects treated with standard care to those treated with ITU plus standard of care. Diagnostic ultrasound imaging will be performed with an FDA approved ultrasound scanner (Spark® System, Ardent Sound, Inc. – Mesa, AZ, see Appendix 6 of proposal) using a coupling gel (Polysonic®, Parker Laboratories, Inc., Fairfield, NJ, see Appendix 7 of the attached proposal) by a trained sonographer or physician. The subject will be positioned prone on an exam table with the feet over the edge of the table. The plantar fascia of the affected and contralateral feet will be imaged. The width and depth of the fascia as well as the size and location of a hyperechoic lesion, when present, will be recorded using both long and short axis imaging. Change in plantar fascia thickness relative to the baseline measurement will be calculated. Decreased thickness of 0.8 mm or greater will be considered clinically significant as these changes have been shown to correlate with decreased pain and increased mobility.

Experimental Treatment: Intense Therapeutic Ultrasound (ITU). Subjects in the ITU group will receive standard treatment plus two treatments (at week 0 and week 2) of ITU to the affected plantar fascia (Table 1 in red). ITU treatment will be performed using a GEN II system (Guided Therapy Systems, Mesa, AZ). (Please see Appendix 5 of the Protocol.) We are seeking classification as a non-significant risk (NSR) device. (Please see the attached NSR statement.) Trained study personnel will conduct the treatments. The treatment session will last 15 – 20 minutes. During this time the subjects will be required to lay prone position on an exam table with their feet hanging over the end of the table. An average energy up to 5 joules / thermal zone will be administered to the symptomatic Plantar Fascia in a linear pattern along the Plantar Fascia (Figure 1) with up to 50 lines. Each line will include individual thermal zones, less than 1 mm³ in volume, centered at 10 – 13 mm depth, and approximately 2 mm apart.

[figure not shown]

Figure 1: The treatment site located around the insertion of the plantar fascia onto the posterior process of the calcaneus

Assessment of Safety and Tolerability (Aim 3). Subject self-assessments of treatment tolerability will be conducted immediately after, two days after (phone survey) and two weeks after treatment using a 10-point visual analog scale (VAS, see Appendix 1-C). The subject will be asked to report their current level of pain and the maximum level of pain experienced over the last two days. The VAS is the standard for assessing pain for both clinical and research purposes. Recording of adverse events will take place at all visits (see adverse event reporting form Appendix 4 in the protocol). Adverse events and serious adverse events will be monitored throughout the study. A treatment will not be administered if there is residual pain/discomfort experienced by the subject from the previous treatment.

Statistical analysis. Data will be assessed for variance homogeneity and normality. FFI-P, PFCAT, and FAAM scores before and after intervention will be compared between the two groups using a paired t-test. Additionally, the mean thickness of the plantar fascia will be compared between the two groups before and after treatment and significance determined utilizing paired t tests. P<0.05 is considered to be statistically significant.

8) Risks to subjects

Exposure to ITU may produce short-term sensations which may cause discomfort and mild erythema for up to a few hours following the exposure. No detrimental side effects have been reported in previous clinical trials investigating similar devices in which ultrasound energy was applied to the neck and face. Additionally, the ITU in this investigation will utilize lower power parameters than those reported for these similar devices. We are seeking classification of the GEN II system (Guided

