Interested individuals who contact the laboratory will have the logistics of the study explained and be referred to the clinic for diagnosis and treatment of heel pain. All patients diagnosed with plantar fasciitis by participating physicians will be contacted by the research team to discuss the details associated with participation. We would like to obtain a temporary deferment of authorization to obtain contact information from the electronic medical record for those individuals who are initially identified in the clinics by participating physicians. Additionally, we would like permission to provide the consent and authorization forms and other information by e/mail should this be conducive to obtaining informed consent. The mailing is for informational purposes only to allow the subject more time to consider participation in the study. The informed consent process will be completed in person. Both English and Spanish versions of the consent forms will be utilized, although the Spanish consent form will be submitted as a modification once the English version is approved. Finally, we would like to provide a map and information sheet to assist participation in the study (see attachments).

7) Procedures involved in the Human Research

After obtaining informed consent and authorization from the subject, study personnel will verify the screening of participants utilizing the inclusion/exclusion criteria and collect the following information- age, gender, height, weight, activity level, pain level, and physical exam findings including x-rays - which will be recorded on the data abstraction sheet (see attachment). The activities strictly associated with the research are the assignment to a study group (Control or ITU), the administration of patient reported outcome measures (questionnaires), and therapeutic and/or diagnostic ultrasound (Table 1). Additionally, adverse events will be recorded at each visit (see attachment). Treatment tolerability will be prior to, immediately after, and at 2 days post-treatment.

Standard of care is integrated into both arms of the investigation and includes a structured physical examination, the use of an NSAIDs for 3 weeks (Naprosyn 500 mg po bid or Ibuprofen 800 mg po tid taken with meals), viscoelastic heel cups for 12 weeks, and supervised physical therapy with home exercise program for 6 weeks. These components are described below-

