**FORM: Application for Human Research**

NUMBER	FORM DATE	PAGE
F200		10 of 18

Table 1. Calendar of Activities

Timeline	Standard of Care	Research Activity
-1	focused history, x-rays, NSAIDs, heel cups	Informed consent and assessment of inclusion/exclusion criteria; enrollment in the study (randomization to treatment group)
0	NSAIDs, heel cups, focused exam	questionnaires; ultrasound (diagnostic & treatment)
2 weeks	NSAIDs, heel cups, focused exam	questionnaires; ultrasound (diagnostic & treatment)
4 weeks	heel cups, focused exam	questionnaires ultrasound (diagnostic)
6 weeks	heel cups, focused exam	questionnaires ultrasound (diagnostic)
12 weeks	heel cups, focused exam	questionnaires ultrasound (diagnostic)
24 weeks		questionnaires

Structured physical examination. The focused exam will consist of assessment of hindfoot and midfoot alignment, inspection for swelling, palpation of the calcaneus and entire plantar fascia, range of motion of the ankle with the knee flexed and with the knee extended, and calcaneal squeeze test. Pertinent positive findings on exam include: valgus hindfoot, midfoot planus, tenderness to palpation at the insertion of the plantar fascia onto the calcaneus, ankle dorsiflexion less than 10 degrees with the knee extended or greater than 10 degree augmentation in ankle dorsiflexion with the knee flexed. Pertinent negative findings include: lack of swelling at the ankle and midfoot, no tenderness at the Achilles insertion, the retrocalcaneal bursae, along the arch, posterior to the medial malleolus, or at Baxters point, and positive calcaneal squeeze test.

Physical Therapy. Supervised physical therapy will occur two times per week and include gastrocnemius stretching, plantar fascia specific stretching, modalities (ice and heat), and plantar fascia deep tissue massage (see instructions to PT appendix 2 of the protocol). Use of advanced modalities such as iontophoresis, phonophoresis, or TENS will not be permitted. The home exercise program will consist of PF specific stretch and gastrocnemius stretch to be done for ten minutes two times per day (see home exercise program handout, Appendix 2 of the protocol). Subjects will be required to record the frequency of each exercise in a logbook (see Appendix 3 of the protocol).

The research components are described below-

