## Statistical Approach

- Pain Reduction:

Pain level at the plantar fascia was self-reported by subjects at pre-treatment (used as baseline measurement) and again at each follow-up - 4, 8, 12, and 26 weeks - after initial treatment. The pain scale subjects used to identify their level of pain was a 10-point pain scale range, where 0 = no pain, 1 = slight pain through 10 which equates to the patient's worst imaginable pain. The goal for all subjects in the treatment group was to reduce pain by at least 25%. Pain scores reported at follow-up timepoints were compared to baseline score for each subject to determine if the goal was met by dividing the difference in the follow-up and baseline pain score by the baseline pain score. The percentage of subjects that met the pain reduction goal was calculated at each timepoint for both control/sham-treated and treatment groups by dividing the number of subjects that achieved the pain reduction goal at each timepoint by the total number of patients that gave a pain score for that time point.

- Plantar Fascia Hypoechoic Lesion Size:

A large proportion of patients suffering from chronic plantar fasciitis present with hypoechoic lesions in or around the proximal plantar fascia, as viewed by diagnostic ultrasound imaging[7].

Hypoechoic lesions were imaged and volumes were calculated at the baseline visit and each follow-up visit by measuring the inferior-to-superior and posterior-to-anterior radii in the long axis and the medial-to-lateral radius of the transverse axis and applying the following formula for the volume of an ellipse:

$$\text{Volume} = (4/3)\pi \cdot r_1 \cdot r_2 \cdot r_3$$

With  $r_1$ ,  $r_2$ , and  $r_3$  representing the three radii detailed above. Changes to lesion volumes were recorded at each follow-up timepoint and compared to baseline by dividing the volume of the lesion at that timepoint with the volume of the same lesion at pre-treatment baseline.

- Foot Function Index Score Reduction:

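### The protocol text and Table 1 disagree on a questionnaire before treatment, so the SAP's baseline is not identified, and no planned test uses baseline as a covariate

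*Protocol*

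**What the plan says.** Protocol Section 3, item 7, Patient Reported Outcome Measures (Aim 1), has subjects complete the questionnaires "prior to initiating treatment and at 0, 2, 4, 6, 12, and 24 weeks after starting treatment".

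Table 1 (Calendar of Activities) differs. At row -1 the standard-care column reads "focused history, x-rays, NSAIDs, heel cups" and the research column reads "Informed consent and assessment of inclusion/exclusion criteria; enrollment in the study (randomization to treatment group", with no questionnaires. They first appear at row 0, as "questionnaires; ultrasound (diagnostic & treatment", and the order within that visit is not given. Row -1 carries no unit.

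The opening paragraphs of item 7 describe "the use of an NSAIDs for 3 weeks" and "viscoelastic heel cups for 12 weeks", and say: "Standard of care is integrated into both arms of the investigation". They also have staff record a pain level and an activity level after consent, with no instrument named.

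The SAP, under Pain Reduction, takes pain "at pre-treatment (used as baseline measurement" and counts the subjects whose score falls by at least 25% from it. Foot Function Index results are percentage reductions from the baseline average. Under Statistical Calculations, t-tests compare baseline with each follow-up. The protocol's Statistical analysis paragraph names paired t-tests. Neither document plans an analysis adjusted for baseline.

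**The concern.** A coordinator who works from Table 1 gives six questionnaire sets. One who works from the text gives seven. The set in dispute is the earliest, and it may fall before or after standard care begins.

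Every result in the SAP is a change from baseline within an arm, so the choice of reading affects the reported percentages and the share of subjects who meet the goal. The order within the week-0 visit matters as well: a score taken after the first ITU or sham session may already carry an effect of that session and is then not a clean baseline.

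The plan also leaves precision unused. The pilot has a target of 50 subjects, and the pre-session score, which costs nothing extra, does not enter any between-arm model.

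**Working it through.** **1. Schedules side by side.**

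| Source | Questionnaire occasions | Count |
|---|---|---|
| Aim 1 text | before treatment; weeks 0, 2, 4, 6, 12, 24 | 7 |
| Table 1 | weeks 0, 2, 4, 6, 12, 24 | 6 |

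The occasion missing from Table 1 is the one before treatment.

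**2. Does standard care start at -1?** Suppose -1 means week -1. NSAIDs listed at -1, 0 and 2 span 2 - (-1) = 3 weeks, which agrees with the stated 3. Heel cups listed from -1 to 12 span 12 - (-1) = 13 weeks, against the stated 12. The early start is therefore well supported for NSAIDs and less certain for heel cups. The heel-cup entries need to be reconciled.

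**3. Why the reading matters within an arm.** The SAP divides the change by the baseline score. Take invented scores of 6 at -1, 5 at week 0 and 4 at follow-up:
- from -1: (6 - 4)/6 = 33%, goal met;
- from week 0: (5 - 4)/5 = 20%, goal missed.

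This shows only that the result depends on the reference. It does not show that either reference is wrong.

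**4. Between-arm comparison.** Both arms have the same standard care and allocation is random, so a shift caused by NSAIDs or heel cups is the same in expectation in each arm. Table 1 puts randomization at -1, so the week-0 score is taken after allocation. Subjects are blinded and no ITU has been given by then, so the score remains usable as a covariate if it precedes the session.

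**5. Gain from covariates.** The documents give no standard deviation or correlation. Assume unit variance and a common correlation r among the -1, week-0 and follow-up scores. The residual variance is:
- no covariate: 1;
- week-0 score: 1 - r²;
- both scores: 1 - 2r²/(1 + r).

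| r (assumed) | Week-0 only | Both | Further cut from second score |
|---|---|---|---|
| 0.3 | 0.910 | 0.862 | 5.3% |
| 0.5 | 0.750 | 0.667 | 11.1% |
| 0.7 | 0.510 | 0.424 | 17.0% |

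The week-0 score alone removes r² of the variance of an unadjusted follow-up score: 9%, 25% and 49%.

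**6. On the scale of a detectable difference.** The plan states no power calculation to reproduce. Assume 25 per arm, two-sided 0.05 and 80% power. The detectable difference in SD units is (1.960 + 0.842) × √(2 × residual variance / 25).
- Without a covariate: 0.792.
- Moving from one score to two: 0.756 to 0.736 (r = 0.3), 0.686 to 0.647 (r = 0.5), 0.566 to 0.516 (r = 0.7).

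**The case against.** The strongest reply is that *treatment* may mean the first ITU or sham session. The protocol often uses the word for the ultrasound sessions, and the SAP counts its follow-up from an initial treatment in the same sentence that defines baseline. On that reading, a score taken before the week-0 session is the pre-treatment baseline, and the Aim 1 text may simply name one assessment twice. This stands as a possible reading. It still leaves the text and Table 1 to be aligned and the order within the week-0 visit to be stated.

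A reader might go further and infer that the only baseline is taken on standard care, that a second baseline is lost, and that the SAP's reductions are therefore wrong. The documents do not support this:
- Nothing says that Table 1 overrides the text.
- A pain level is also recorded after consent and could be the SAP's score. The SAP's follow-up weeks (4, 8, 12, 26) do not match Table 1, so its baseline cannot safely be read off that table.
- Pain at -1 is not shown to be untreated pain. Entry requires three months without improvement, and no listed criterion requires subjects to be free of earlier care.
- For the effect of adding ITU to standard care, a pre-session week-0 score is a sound reference, arguably better than an earlier one.

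It is also fair to say that the precision gain belongs to an analysis that the plan does not contain. It measures what an added analysis would bring and is not a cost of the mismatch itself.

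**Conclusion.** This is a minor point that is cheap to settle. The two schedules conflict, and the SAP's baseline cannot be identified from the documents. The between-arm comparison is not biased by when standard care starts, given randomization and the same care in both arms. Using the week-0 score as baseline requires that it precede the session. Within-arm reductions and the 25% goal do depend on which reading is used.

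Adjusting for the week-0 score is the larger gain. The earlier score adds a further cut in residual variance of about 5%, 11% or 17% at assumed r of 0.3, 0.5 or 0.7. These are upper-end figures: a reading at -1 and one at week 0 with NSAIDs started are not true replicates, and estimating another slope from 50 subjects uses a little information.

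**What to change.** 1. Reconcile the Aim 1 text with Table 1 by adding the questionnaires at the -1 visit, completed before standard-care items are dispensed. Give the unit of -1, and reconcile the heel-cup rows with the stated duration.
2. State that week-0 questionnaires precede the ultrasound session.
3. In the SAP, define *pre-treatment* and name the week-0 pre-session score, with its instrument, as the pre-ITU baseline for the percentage reductions and the 25% goal.
4. Compare each questionnaire outcome between arms by analysis of covariance, with arm, the week-0 score and, where collected, the -1 score in the model.

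The cost is one extra questionnaire set per subject, at an existing visit or online (the protocol already allows online completion), plus wording in both documents. The SAP is written in the past tense. If collection is complete, step 1 can only correct the record, but steps 3 and 4 remain possible with the week-0 score, provided records confirm that it preceded the session.

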**FORM: Application for Human Research**

NUMBER	FORM DATE	PAGE
F200		8 of 18

3) Setting of the Human Research

The PI is an assistant professor in the Department of Orthopaedic Surgery and surgeon with the University of Arizona Health Network. Subjects will be recruited from the outpatient clinic of Drs. [name] (PI) and [name]. The age, gender, height, weight, activity level, pain level, and physical exam findings of patients will be obtained directly from the subject, the subject's medical record, or from direct examination and then recorded in a password protected excel file. The online survey can be completed from any computer available to the subject. Intense therapeutic ultrasound and diagnostic ultrasound will be administered in the Human Movements Biomechanics Lab (BRL B101).

4) Resources available to conduct the Human Research

Equipment for intense therapeutic ultrasound will be provided by [name] and [name] from Guided Therapy Systems. The equipment for measuring height and weight will be in the orthopedic clinic. Personnel available to conduct the study include 2 surgeons, 1 clinical research coordinator, 2 sonographers, 1 medical student, and 2 undergraduate assistants. These individuals will be available to recruit and consent patients, coordinate and conduct the study, analyze the data, and produce a manuscript.

5) Study Population

Male and female adults (18 years or older) with plantar heel pain and point tenderness near the medial calcaneal insertion of the plantar fascia for at least three months without improvement will be considered for inclusion into the study. Subjects with diabetes, bilateral plantar heel pain, current systemic or local infection, previous foot surgeries, other foot/ankle pathologies (inflammatory arthritis, gout, neurologic disorders, connective tissue disorders and malignancy), contraindications to the use of NSAIDs, and pregnancy will be excluded. The target enrollment of this pilot study is 50 participants.

6) Recruitment Methods and Consenting Process

Subjects will be recruited utilizing public media, list serves, community organizations, and via referral. Please see the attachments to this application for an electronic media and brochure representations of the advertisements to be utilized. We would like to select from the following wording to produce recruitment materials -

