In addition to the 11-point VAS pain scale, patients self-reported answers to questions from the Foot Function Index (FFI) pain subscale questionnaire, which has been standardized in a number of PF-focused publications [8-10]. Scores range from 0-90, with 0 indicating no pain and 90 indicating the worst pain imaginable in a variety of daily activities involving use of the plantar fascia. Self-reported scores were taken at baseline and each follow-up timepoint. The average score for each timepoint were calculated, and follow-up averages were compared to baseline to calculated the percentage reduction in score.

- Statistical Calculations

Student T-tests were utilized to determine statistically significant differences between baseline and subsequent follow-up measurements for self-reported and lesion size measurements. The level of significance ( $\alpha$ ) was set to 0.05.

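### The protocol scans both feet of subjects with one-sided heel pain, but no stated analysis uses the other foot; its baseline thickness could be a covariate in the Aim 2 comparison at almost no cost.

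*Protocol*

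**What the plan says.** The Aim 2 paragraph (Protocol, Section 3, item 7, Diagnostic Ultrasound) states: "The plantar fascia of the affected and contralateral feet will be imaged". It then says "Change in plantar fascia thickness relative to the baseline measurement will be calculated" and sets a threshold: "Decreased thickness of 0.8 mm or greater will be considered clinically significant". The reason given for the threshold is that "these changes have been shown to correlate with decreased pain and increased mobility". The paragraph does not say at which visits the second foot is scanned, or which foot the change refers to.

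Table 1 lists diagnostic ultrasound at weeks 0, 2, 4, 6 and 12, again without naming a foot. The Study Population item makes the disease one-sided; its exclusions begin "Subjects with diabetes, bilateral plantar heel pain, current systemic or local infection".

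The protocol's Statistical analysis paragraph says that "the mean thickness of the plantar fascia will be compared between the two groups before and after treatment", with paired t tests and no covariates. It names no foot.

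The SAP's Statistical Calculations read: "Student T-tests were utilized to determine statistically significant differences between baseline and subsequent follow-up measurements for self-reported and lesion size measurements". Fascia thickness, the contralateral foot and the 0.8 mm threshold appear nowhere in the SAP. Its imaging measure is lesion volume.

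**The concern.** A measurement is collected on every subject and then given no stated purpose. The other foot's baseline thickness could carry information on how far the affected fascia can thin. The protocol's Background quotes study means of 2.3 to 4.0 mm without the disease and 4.8 to 6.5 mm with it. Unaffected means thus span 1.7 mm across studies (4.0 − 2.3), although some of that spread may come from differences in method. If the subject's own other foot predicts follow-up thickness beyond what the affected foot's baseline predicts, leaving it out leaves removable variance in a small comparison.

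There is a second, lesser issue. The 0.8 mm threshold rests on its relation to symptoms, and the supplied documents give no scan repeatability. A reader cannot tell whether a fall of that size in one subject is distinguishable from measurement error.

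**Working it through.** There is no stated figure to reproduce: the plan gives no power calculation, no SD of thickness, no between-foot correlation and no scan error.

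**Inputs from the protocol.** 50 subjects, allocated 1:1 (25 per arm if all are evaluable); significance level 0.05, taken as two-sided; threshold 0.8 mm; up to five imaging visits (baseline and four follow-ups).

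**Assumed inputs.** Partial correlation r between baseline contralateral thickness and follow-up affected thickness, given baseline affected thickness; between-foot correlation ρ of the changes; SD 1.0 mm for the power illustration; the standard error of measurement (SEM) of a single scan.

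**1. Gain from the covariate.** Residual variance is multiplied by 1 − r², and the equivalent sample size is 50/(1 − r²).
- r = 0: factor 1.00, equivalent to 50 subjects, no gain.
- r = 0.2: factor 0.96, 50/0.96 = 52 subjects, 4% less variance.
- r = 0.5: factor 0.75, 50/0.75 = 67 subjects, 25% less variance.

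For a 0.8 mm difference with residual SD 1.0 mm and 25 per arm, power = Φ(0.8/(SD × √(2/25)) − 1.96). This gives 80.7% at r = 0, 82.3% at r = 0.2 and 90.4% at r = 0.5. The cost is two degrees of freedom for the two covariates: 50 − 2 = 48 residual without them, 46 with them.

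**2. Subtracting the other foot's change instead.** With equal SDs the variance factor is 2(1 − ρ): 2.0, 1.4, 1.0 and 0.6 at ρ = 0, 0.3, 0.5 and 0.7. By the same formula, power is 51.6%, 66.7%, 80.7% and 95.5%, against 80.7% for the affected foot alone. Subtraction loses precision whenever ρ is below 0.5.

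**3. The 0.8 mm threshold against scan error.** The 95% limit for the difference of two scans is 1.96 × √2 × SEM. Setting it to 0.8 gives SEM = 0.8/(1.96 × 1.414) = 0.289 mm. The chance that an unchanged fascia shows a fall of 0.8 mm or more at one visit is Φ(−0.8/(√2 × SEM)): 3% at SEM 0.3 mm, 8% at 0.4 mm and 13% at 0.5 mm.

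**4. Could the contralateral scans estimate the SEM?** If all 50 subjects have all five scans, there are 50 × 4 = 200 degrees of freedom, and the 95% interval for the SEM runs from about 9% below to 11% above the estimate. Using weeks 4, 6 and 12 only, which fall after the three-week NSAID course, gives 50 × 2 = 100 degrees of freedom and about −12% to +16%.

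**The case against.** The strongest reply is that this is an unused opportunity, not an error. Omitting an optional covariate does not bias a randomised comparison, and no correlation in the documents shows that precision is lost. That stands, and it limits the claim to precision that may be forgone.

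Four stronger readings are tempting, and the documents do not support them.

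- A reader might infer that the second foot is scanned at all five visits. The Aim 2 paragraph names no visit for it. If only baseline is scanned, the covariate is still available but no SEM can be estimated.
- A reader might infer that the contralateral foot is definitely excluded from analysis. The statistical paragraph names no foot, so the most that can be said is that no stated analysis uses it. The protocol's appendices and the separate ITU protocol in the attachment list were not supplied, so an imaging or repeatability procedure there cannot be ruled out.
- A reader might infer that scan error will produce many false responders. For a fall at any of four follow-ups, simulation gives 21% at SEM 0.4 mm and 32% at 0.5 mm. Neither document plans a 0.8 mm responder analysis or an any-visit rule; the planned comparison is of means. Random error of similar size in both arms adds noise to a difference in means but does not create one.
- A reader might take the other foot as a clean yardstick. Both arms take a systemic NSAID for three weeks, so the foot may really change, which would inflate the SEM. Conversely, error in a thinner fascia may differ from error in a thickened one. Absence of heel pain does not prove normal thickness. Repeat scans within a visit would be cleaner, but would be new work.

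**Conclusion.** The point holds as a low-cost improvement to one imaging aim of a pilot. Both feet are imaged, no stated analysis uses the contralateral scan, the protocol's thickness comparison is unadjusted, and the SAP omits thickness altogether. The between-arm comparison is not biased by this. The possible gain is 4% to 25% less variance if the partial correlation is 0.2 to 0.5, and nothing if it is 0; that range is an assumption. The absence of any thickness analysis from the SAP is the more basic gap, since without one there is no model to which a covariate can be added.

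The threshold issue is secondary. Clinical relevance and detectability in one subject are different questions, and the protocol addresses only the first. The 0.29 mm limit is arithmetic; whether the scans meet it cannot be judged from the documents.

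**What to change.** In the protocol's Statistical analysis paragraph and in the SAP:

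1. State that Aim 2 analyses the affected foot, and say why the contralateral foot is scanned and at which visits.
2. Compare follow-up affected-foot thickness between arms by ANCOVA, with baseline affected thickness and baseline contralateral thickness as covariates. This replaces the paired t tests for the between-arm question and puts a thickness analysis into the SAP.
3. Optional, once scanning of the second foot at every imaging visit is confirmed: report its between-visit SEM and smallest detectable change (1.96 × √2 × SEM) beside any statement that uses 0.8 mm. Label this an approximate upper estimate of scan error, with the caveats on NSAIDs and thinner fascia.
4. Leave out side-to-side subtraction, or label it exploratory and state that with equal SDs it loses precision when the between-foot correlation is below 0.5.

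The cost is one degree of freedom per covariate, a new thickness section in the SAP and a short analysis. Items 1 and 2 need no new scans, staff or visits. The SAP is written in the past tense, so if thickness data have already been examined, the adjusted model should be labelled as specified afterwards.
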